### **10.7.4 Risks of QMT**

QMT will be done at each visit to measure strength in the participant's muscles. At this time, there are no known risks associated with functional evaluation or muscle strength testing methods used in this protocol. However, the participant may experience mild muscle soreness the day after muscle testing.

### **10.7.5 Risks of PFT**

These tests may cause dizziness and lightheadedness during and shortly after the test.

### **10.7.6 Risks of EKG**

The EKG has no known risks.

### **10.7.7 Risks of Functional Evaluation and Muscle Strength Testing**

At this time, there are no known risks associated with functional evaluation or muscle strength testing methods used in this protocol. However, the participant may experience mild muscle soreness the day after muscle testing.

### **10.7.8 Risks of DEXA**

DEXA scans involve exposure to a very small amount of radiation (<1.0mrem). DEXA is contraindicated in pregnancy (not applicable in this project).

### **10.7.9 Risks of Multi-Frequency Bioimpedance Assessment (MFBIA)**

There are no known risks of MFBIA testing.

### **10.7.10 Risks of Upper Extremity Range of Motion Evaluation**

There are no known risks of upper extremity range of motion evaluation.

## **10.8 Procedures for Minimizing Risks**

Confidentiality of medical information will be maintained throughout the study. Participants will be assigned identification numbers that will be used on all case report forms. No personally identifiable information will be released beyond the Study Coordinating Center without the participant's prior written consent. Data entered into electronic case report forms will be handled by the RedCap online CRF system and managed in compliance with FDA privacy and data retention standards for electronic clinical research data collection.

Safety data recorded during the conduct of this study will be transmitted directly to the Medical Monitor through the RedCap system. Data will be collected at each study visit and over the phone (family reported AEs) between study visits. Both AEs and SAEs will be reviewed by the Medical Monitor. AEs will be reviewed on a quarterly basis by the Medical Monitor.

## **10.9 Justification of Risks to Participants**

Due to the low toxicity profiles of (-)-epicatechin, risks to subjects associated with participation in this study are less than or similar to standard clinical interventions in patients with BMD.

## **10.10 Benefits**

The intended benefits outweigh the risks of using the study medication and study procedures in BMD patients. The participants may experience an increase in muscle strength or a delay in strength decline. The participants will receive additional care during study participation including muscle strength training, contracture measurements and spirometry during each study visit. Medical and adverse event history will be closely monitored. The additional medical monitoring allows for increased interaction with medical staff above expected routine clinical care. The increased monitoring of safety labs will also be performed.

It is possible the participants will not experience any direct benefit as a result of their study participation. However, the data collected during this trial may provide information that will benefit the scientific community as well as other individuals with BMD

## **10.11 Financial Considerations**

No financial compensation will be given to participants or their families for participation in this trial other than minor assistance with transportation expenses (parking, etc.).

## **11 STATISTICS**

Presented herein is the overall analysis plan. The main criterion for success of the study will be presence of one or more biologic or strength and performance outcome measures (Aims 1 and 2) that yield a response magnitude that allows for sufficient power in a Phase II B study with a sample size of 30 individuals. Analysis, employing both statistical and graphical presentations of data, will generally proceed from descriptions and simple comparisons to multiple variable models. This will help to ensure proper understanding of the data at each level before proceeding to the next. Descriptive analysis of means and proportions will characterize study participants overall as well as evaluate assumptions of normality and homoscedasticity. Any significant departures from these assumptions especially for the measurement variables will lead to normalizing or variance stabilizing transformations or, in the unlikely event these are not successful, to conversion to ranks. Baseline and screening measures will be used to calculate test-retest reliability using the intraclass correlation coefficient. Level of statistical significance is set at  $<0.05$ . Simple comparative analyses involving chi squares ttests and correlations will be used to assess and understand simple relationships, including defining first order interactions. Where possible we will perform longitudinal analyses using mixed models (using xtreg or xtmixed in STATA 12) to evaluate raw scale and percent change over time in study outcomes measures. These procedures will allow us to account for fixed and random effects as well as correlation between observations when we introduce repeated measures on the same individuals. If feasible with the small number of participants in the study and because there is little available data for individuals with Becker muscular dystrophy, this pilot data will be used to determine estimates of minimally important clinical difference (MCID) for each measure (defined as  $1/3$  S.D. for the population). Safety data will be compiled as tables of frequency and severity of adverse events by body system.

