## 6 RESEARCH DESIGN AND METHODS

### 6.1 Selection and Withdrawal of Participants

#### 6.1.1 Criteria for Enrollment

Ten participants will be studied in this initial pilot project.

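### Section 11 lets an unspecified check in ten men decide, after the data are seen, whether each marker is analysed raw, transformed or ranked, and does not say which scale supplies the success magnitude

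*Combined protocol and SAP*

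**What the plan says.** The trial is small: "Ten participants will be studied in this initial pilot project" (Section 6.1.1), open-label and single-arm. Section 11 holds the whole analysis plan.

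- The descriptive analysis will "evaluate assumptions of normality and homoscedasticity", within an approach "employing both statistical and graphical presentations of data".
- The consequence is: "Any significant departures from these assumptions especially for the measurement variables will lead to normalizing or variance stabilizing transformations".
- If transformation fails, the plan moves, "in the unlikely event these are not successful, to conversion to ranks".
- "Level of statistical significance is set at" <0.05. This is stated for the analysis generally and is not tied to the distribution check.
- Success requires at least one Aim 1 or Aim 2 measure to "yield a response magnitude that allows for sufficient power in a Phase II B study with a sample size of 30 individuals".
- Mixed models of raw-scale and percent change are also planned where possible.

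Section 11 does not name a test or a transformation. It does not say whether raw values, within-person changes or model residuals are checked, what would make a transformation successful, or which scale feeds the success criterion once a measure has been transformed or ranked.

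**The concern.** Many outcomes in Sections 1.4 and 8.1 are of a kind that usually varies multiplicatively: CPK, follistatin, Western blot densities, epicatechin metabolite concentrations and lactate. For these the natural summary is a ratio, and the log scale can be chosen before any data exist. Section 11 instead lets the sample decide, one marker at a time. That raises three problems.

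1. Ten observations say little about distributional shape. A marker may be logged or left raw largely by chance, and related proteins in the same blot panel may end up on different scales.
2. Success is defined by a magnitude, and one qualifying measure is enough. If the magnitude can be read on more than one scale, the scale becomes a free choice made after the data are known, in a trial with no blinding.
3. A rank analysis yields no change in natural units to carry into a power calculation or to set against the Aim 2 thresholds in Section 1.4.

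**Working it through.** The documents give no SD, skewness or correlation for any outcome and no error rate for the check, so there is no planned figure to reproduce. Only n = 10, the 0.05 level and the Phase IIB size of 30 come from the documents. The distributions below are assumptions, shown over a range.

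**Step 1. What a 5% normality test detects at n = 10.** For lognormal data, log-SD = √ln(1 + CV²). Simulated Shapiro-Wilk rejection rates:

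| CV | log-SD | Rejects | Misses |
|---|---|---|---|
| 40% | 0.39 | 17% | 83% |
| 60% | 0.56 | 29% | 71% |
| 80% | 0.70 | 40% | 60% |
| 100% | 0.83 | 49–51% | 49–51% |

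Beyond this range the miss rate falls: 41% at log-SD 1.0 and 18% at 1.5. The D'Agostino skewness-kurtosis test does worse there, missing 51% and 34%. When Shapiro-Wilk is applied to raw post-minus-pre differences (log-scale correlation 0.5–0.8), it misses 83–86% at log-SD 0.5 and 58–61% at 1.0.

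**Step 2. Cost in power.** Model: log value = person effect (between-person log-SD b) + visit error (log-SD w) + log of the fold change at follow-up. Paired t-test, n = 10, two-sided 0.05. The log-scale standardised effect is ln(fold)/(w√2):

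- b 0.4, w 0.2, 1.3-fold: 0.262/0.283 = 0.93
- b 0.6, w 0.25, 1.3-fold: 0.262/0.354 = 0.74
- b 0.8, w 0.3, 1.4-fold: 0.336/0.424 = 0.79

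Simulated power for a log scale fixed in advance, against taking logs only if Shapiro-Wilk gives p < 0.05:

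| Case | Log fixed in advance | Check on baseline | Check on differences | Baseline, follow-up or difference may trigger |
|---|---|---|---|---|
| 1 | 74–75% | 69–70% | 70% | 72% |
| 2 | 55–56% | 48–49% | 50% | 53% |
| 3 | 61% | 52–53% | 54% | 59% |

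The loss is about 2–3 points if any of the three can trigger logs, and about 4–9 points if only one set of values is checked. With no true change the rule rejects about 4–5% of the time, so type I error is not the problem.

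**Step 3. Percent change.** In this model the log ratio has variance 2w², so with no true change the expected ratio is exp(2w²/2) = exp(w²). The expected mean percent change is then:

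- w 0.2: exp(0.04) − 1 = +4.1%
- w 0.25: exp(0.0625) − 1 = +6.4%
- w 0.3: exp(0.09) − 1 = +9.4%

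**Step 4. Bearing on the success criterion.** Section 11 gives no power level, test or design for the 30. Assuming 80% power and two-sided 0.05, the detectable standardised change is (1.96 + 0.84)/√30 = 0.51 for 30 paired subjects, or (1.96 + 0.84) × √(2/15) = 1.02 for 15 v 15. In the three cases the median standardised change at n = 10 was 0.86 raw v 0.96 log, 0.66 v 0.77, and 0.63 v 0.83. The two scales disagreed on whether a marker passed 0.51 in roughly 6%, 14% and 20% of simulated trials.

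**Step 5. Ranks.** For ten illustrative differences (1, 2, 3, −0.5, 4, 5, 6, −1.5, 2.5, 3.5) the mean is 2.5 and the signed-rank p is 0.0137. Changing the 6 to 60 moves the mean to 7.9 and leaves p at 0.0137. The rank result carries no magnitude in natural units.

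**The case against.** The strongest reply is that Section 11 states no formal normality test. It plans graphical as well as statistical review, and looking at distributions before settling a scale is ordinary practice in a pilot meant to develop endpoints. This stands as far as it goes: a reader might infer from the word significant that a 5% test triggers the change, but the text does not say so, and the figures in Steps 1 and 2 are conditional on that reading. A purely visual check would be more discretionary, so the case for fixing the scale remains.

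A reader might also infer that any such test misses skew at least half the time. That fails for severe skew, as Step 1 shows.

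Nor does the rank step remove the response magnitude from the plan. It is a second fallback that the protocol calls unlikely, and raw-scale and percent-change models are planned where possible. What is missing is a statement of which of these the success criterion uses.

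Finally, percent change is itself a relative scale, already planned and not made conditional on the check. In the same three cases a one-sample t-test on percent change had power of 78%, 60% and 65%, above the fixed log scale, with type I error 5.0–5.2%. That is a fair point on power alone. But its mean is shifted upward by 4–9% with no true change, which is consistent with the power edge. Success turns on the size of the response, so a summary that overstates that size is not a substitute.

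**Conclusion.** The concern holds in a limited form. Section 11 leaves the scale of each measure to an unspecified check in ten men, made after the data are seen, and does not say which scale supplies the magnitude on which success depends. If the check is a 5% test, it misses about 50–80% of lognormal samples with CV 40–100%. The resulting loss against a log scale fixed in advance is about 2–9 points of power, with type I error near 5%.

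These sizes rest on lognormal data, between-person log-SDs of 0.4–0.8, visit log-SDs of 0.2–0.3 and true rises of 1.3- to 1.4-fold, none of which the documents give. The comparison with 0.51 also assumes a paired Phase IIB design at 80% power. The absence of a stated scale for the success magnitude depends on none of these assumptions. The documents do not support a claim of inflated false positives, or that the pilot would be left without any response magnitude. The change is worth making because it is cheap and settles a choice that bears directly on the success criterion.

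**What to change.** Add to Section 11, before any analysis:

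- Concentrations and densitometry values (CPK, follistatin, Western blot, PK, lactate) are analysed as natural logs and reported as geometric mean ratios with 95% CI.
- Strength and functional measures stay in raw units.
- These scales supply the response magnitude for the success criterion.
- Distribution checks are applied to within-person changes or model residuals as diagnostics. They do not trigger a change of scale.
- Signed-rank or permutation tests are used only as sensitivity p-values beside the estimate, never in its place.

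The cost is a few sentences, plus a rule for zero or below-detection values, which cannot be logged as they stand. No visit, sample or participant is added.

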## 1.2 Study Purpose

This is a proof-of-concept phase 1/2a pilot and endpoint development study that is designed to provide initial evidence of biological activity of (-)-epicatechin. Primary endpoints include initial assessment of tissue-specific evidence of efficacy from muscle biopsy samples. Secondary endpoints include measures of strength and physical function, and safety and adverse event data. Pilot endpoints include assessment of mRNA and miRNA peripheral blood profiles and validation of non-invasive near-infrared spectroscopy (NIRS) muscle perfusion studies during exercise and a recumbent cycle exercise test that may be employed as endpoints in future clinical trials.

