## 1.4 Specific Aims

**Aim 1. (Efficacy Primary Endpoint): Evaluation of (-)-epicatechin on blood and muscle tissue markers of mitochondrial biogenesis and muscle regeneration in adults with Becker muscular dystrophy.** Treatment with 8 weeks of (-)-epicatechin 100mg daily will induce mitochondrial biogenesis, muscle regeneration, and improved histological appearance in sarcomere morphology.

*Hypothesis:* (-)-Epicatechin will show evidence of mitochondrial biogenesis by Western blot assays of biceps brachii muscle biopsies through increases in ETC1, ETC5 and SOD2 proteins.

*Hypothesis:* (-)-Epicatechin will show evidence of induction of muscle regeneration through increases in PGC1a, decreases in acetylated (inactive) PGC1a, and increases in follistatin,

myogenin, and MyoD compared to pre-treatment baseline as determined by Western blot assays of biceps brachii muscle biopsies.

*Hypothesis:* Administration of (-)- epicatechin will be associated with increases in plasma concentrations of follistatin, a known hormonal regulator of muscle regeneration and a potential pharmacodynamic biomarker.

*Hypothesis:* Administration of (-)- epicatechin will be associated with electron microscopy evidence of increases in mitochondrial number and cristae density within the mitochondria compared to pre-treatment baseline.

*Hypothesis:* Administration of (-)- epicatechin will be associated with increased nNOS expression in skeletal muscle compared to pre-treatment baseline and this increased expression will be associated with improved muscle perfusion during exercise.

**Aim 2 (Efficacy Secondary Endpoints): Evaluation of the effects of (-)-epicatechin on exercise capacity in adults with Becker muscular dystrophy.** Individuals with Becker muscular dystrophy who receive 100mg/day of (-)-epicatechin will demonstrate improved exercise performance and strength that is associated with increases in mitochondrial biogenesis and muscle regeneration.

*Hypothesis:* Using the 6 minute walk test, and a standardized recumbent cycle exercise test with measurement of lactic acid levels, VO2 max, Work max, anaerobic threshold, and NIRS-defined skeletal muscle perfusion (measures of oxyhemoglobin, deoxyhemoglobin, and tissue saturation index) we will detect pre-/post-treatment differences in exercise capacity and endurance that will be clinically significant ( $\geq 5$ -10%) and reflect increases in mitochondrial biogenesis.

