*Hypothesis:* Changes in grip strength ( $\geq 5\%$ ), elbow flexion/extension isometric strength ( $\geq 5\%$ ), knee extension isometric muscle strength ( $\geq 1$  pound = 4.448 Newtons), pulmonary function derived maximal static airway pressures (MIP and MEP  $\geq 10$  cm H2O), and regional lean tissue mass by DEXA ( $\geq 2\%$ ) will be clinically significant and correlate with biomarker evidence for muscle regeneration and histological improvement in sarcomere morphology.

*Hypothesis:* Pilot data from exercise performance and strength evaluations in adults with Becker muscular dystrophy will determine the magnitude of response over time that will enable accurate power calculations for future clinical trials.

**Aim 3 (Safety Secondary Endpoints): Evaluation of safety and pharmacokinetic profiles of (-)-epicatechin in adults with Becker muscular dystrophy.** Assessments of safety will include a standard clinical safety panel including hematologic, hepatologic, renal and metabolic profiles. Pharmacokinetic studies will include repeat assessments of trough, 2 hour-post (peak) and 4-hour post dose (-)-epicatechin levels.

*Hypothesis (safety):* (-)-epicatechin given at 100mg/d orally will display an acceptable safety profile in BMD patients.

*Hypothesis (pharmacokinetics):* (-)-epicatechin given at 100mg/d orally in BMD patients will produce pharmacokinetic profiles similar to those seen in previously described studies in the literature.

**Aim 4 (Pilot Biomarker Endpoints): Pilot evaluation of disease- and epicatechin-specific circulating mRNA and miRNA blood profiles as pilot biomarkers for monitoring treatment efficacy.** Epicatechin stimulates follistatin expression in tissue and blood. In addition to its effects on muscle regeneration, follistatin is known to exert anti-inflammatory and anti-fibrotic effects via antagonism of activin and myostatin.

*Hypothesis:* Using gene array assays directed toward fibrosis- and inflammatory-oriented pathways, we expect treatment with (-)-epicatechin to induce detectable pre-/post-treatment differences in mRNA and miRNA expression that may be utilized as biomarkers of treatment effect for future clinical trials.

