#### 6.1.2 Participant Screening Schedule

Potential participants for the study will be evaluated using a two visit screening method that will allow investigators to evaluate the participant's ability to provide a reproducible (15%) (*primary endpoint*) test scores to be enrolled. The entry procedures will be conducted according to the schedule in **Table 3**. After potential participants have completed the screening visits and the site has verified they meet all study inclusion criteria the participant will be randomized into the study.

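### The ICC is the only test-retest statistic planned, and it cannot show whether a measure is precise enough for the percent changes sought in Aim 2

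*Combined protocol and SAP*

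**What the plan says.** On reliability, section 11 has one sentence: "Baseline and screening measures will be used to calculate test-retest reliability using the intraclass correlation coefficient". It names no form of ICC, no confidence interval, no acceptance level and no measure of absolute error, such as a within-person SD, a within-person CV or limits of agreement.

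Three other parts of the protocol bear on this:

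- Section 1.2 lists among the pilot endpoints the "validation of non-invasive near-infrared spectroscopy (NIRS) muscle perfusion studies during exercise and a recumbent cycle exercise test", for possible use in later trials. Reliability is therefore something the study is meant to deliver.
- Section 1.4, Aim 2, expects that "we will detect pre-/post-treatment differences in exercise capacity and endurance that will be clinically significant", and sets this at 5-10% or more. Grip and elbow strength have a threshold of 5%. Knee extension (1 pound), MIP and MEP (10 cm of water) have thresholds in absolute units.
- Section 11 adds that, if feasible, "this pilot data will be used to determine estimates of minimally important clinical difference (MCID) for each measure", with the MCID set at one third of the population SD.

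Section 6.1.2 contains the only other reproducibility requirement: to be enrolled, a man must give scores reproducible to 15% over two screening visits. It gives no formula, and identifies the test only by a bracketed reference to the primary endpoint.

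**The concern.** Aim 2 asks a within-person question: can this measure show a change of a stated size in the same man, or in the mean of ten men? The ICC answers another question, namely what share of the total variance lies between men. Entry is open to men aged 18 to 60 who can walk 75 metres unaided, so between-man spread may well be wide, and a wide spread raises the ICC without any gain in precision. The ICC also has no units, so it cannot be set against 5%, 1 pound or 10 cm of water.

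What is at stake is how the pilot's main methodological product is read. NIRS or the cycle test could be described as reliable on a high ICC while their noise is as large as the change a later trial would look for. The opposite error is possible too: a precise measure in similar men can show a poor ICC.

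**Working it through.** The protocol states no SD, CV, ICC value or measurement error, so there is no figure of its own to reproduce.

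**Inputs.** From the protocol: ten men (sections 1.3 and 6.1.1), the Aim 2 thresholds (section 1.4), MCID = SD/3 and significance level 0.05 (section 11), taken as two-sided. Assumed: between-man CVs of 10 to 50%, and the SD in the retest sample equal to the population SD.

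**1. Dependence on spread.** ICC = B²/(B² + W²), with B the between-man and W the within-man CV. Hold W at an illustrative 8%:

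- B = 10%: 100/164 = 0.61
- B = 20%: 400/464 = 0.86
- B = 30%: 900/964 = 0.93
- B = 50%: 2500/2564 = 0.98

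The same measurement error looks poor or excellent according to who is enrolled.

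**2. Against the percent thresholds, at ICC 0.95.** W = B × sqrt(0.05/0.95) = 0.2294 × B. The 95% half-width for the mean change of ten men, from measurement noise alone, is t(0.975, 9) × sqrt(2/10) × W = 2.262 × 0.4472 × W = 1.012 × W. The 95% limit for one man's retest difference is 1.96 × sqrt(2) × W = 2.772 × W.

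| Between-man CV | Within-man CV | Ten-man half-width | One-man limit |
|---|---|---|---|
| 10% | 2.3% | 2.3% | 6.4% |
| 20% | 4.6% | 4.6% | 12.7% |
| 30% | 6.9% | 7.0% | 19.1% |
| 50% | 11.5% | 11.6% | 31.8% |

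One ICC value is compatible with a group half-width below 5% and with one above 10%.

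**3. Against the MCID.** The measurement error is SD × sqrt(1 − ICC). The ten-man half-width is then 1.012 × sqrt(1 − ICC) in SD units: 0.45, 0.39, 0.32 and 0.23 at ICC 0.80, 0.85, 0.90 and 0.95. It equals 1/3 at ICC = 1 − (0.3333/1.012)² = 0.891. The one-man limit, 2.772 × sqrt(1 − ICC), equals 1/3 at ICC = 1 − (0.3333/2.772)² = 0.986. No CV is needed here, because the MCID and the error scale with the same SD.

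**4. Precision of the ICC.** With ten men measured twice and an observed ICC of 0.90, F = 1.9/0.1 = 19. One-way F limits give a 95% interval of 0.67 to 0.97, which spans the 0.89 crossover.

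**5. Whether the retest pair exists.** Table 3 marks functional assessments at Baseline, Week 4, Week 8 and early withdrawal, but not at Screening. Section 6.1.2 speaks of scores over two screening visits, section 10.7.4 places strength testing at each visit, and section 11 relies on a screening and a baseline value. These do not agree. The muscle biopsy is taken once before treatment.

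**The case against.** A reader might infer that measures will go into the 30-person Phase IIB on the strength of their ICC. The documents do not support that. No decision is tied to the ICC. Success (sections 1.3 and 11) depends on a response large enough to give adequate power with 30 people. That power depends on the SD of the change, which contains measurement error, so a noisy measure is penalised there whatever its ICC. The planned t-tests and mixed models likewise carry noise in their standard errors. All this stands. Those analyses use on-treatment data, however, where noise is mixed with differences in response. They neither isolate retest error nor set it beside a threshold.

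A reader might also infer that an excellent ICC can hide group-level noise larger than the MCID. It cannot: above a true ICC of about 0.89 the ten-man mean clears it. The MCID lies within the noise at higher ICCs only for single men, and the plan makes no claim about individual responders.

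The 15% rule in section 6.1.2 is a within-person criterion and deserves mention. But it screens participants, is wider than the 5-10% sought, and estimates no measure's error.

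Two further points hold in part. The error can be derived from the ICC and the SD, but the plan does not ask for this. And a within-person SD from ten pairs is imprecise, with a 95% interval of about 0.70 to 1.75 times the estimate. That argues for showing the interval and against a pass mark.

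**Conclusion.** The concern holds as a gap in what is reported. The analysis plan's one test-retest statistic does not tell the reader whether a measure can detect the Aim 2 changes, although the study sets out to validate endpoints. The size in percent depends on a spread that the protocol does not give. If between-man CVs are 20% or less, an ICC of 0.95 is adequate for a ten-man mean even at the 5% threshold. At 30% noise alone exceeds 5%, and at 50% it exceeds 10%. The MCID crossovers, about 0.89 for the group and 0.986 for one man, need no CV, but they take the sample SD as the population SD. With ten men, an observed ICC of 0.90 cannot show on which side of the group crossover a measure lies. The point does not undermine the pilot's success criterion.

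**What to change.** In section 11, replace the reliability sentence with wording to this effect: *for every measure with two pre-treatment values, the main reliability result is the within-person SD, and the within-person CV from log-transformed values, each with a 95% CI. The 95% limit for a retest difference and the noise half-width for a ten-man mean change will be tabulated beside the Aim 2 threshold and the MCID. The ICC, with its form and 95% CI stated, is secondary.* Describe the validation of NIRS and the cycle test in the light of that table, without a hard cut-off.

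Reconcile Table 3 with sections 6.1.2, 10.7.4 and 11, so that it is clear which functional measures are taken twice before treatment. The planned ICC needs the same pair. Biopsy markers have a single pre-treatment sample and fall outside this change.

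The cost is a few sentences, a few lines of code and one table. No extra data are needed for measures that already have a pair. If the functional tests are in fact not done at Screening, a retest result for them would need an added session. The estimates will be imprecise, and some measures will look less favourable than their ICC suggests.
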